 - d) Document any ethical /unexpected issues emerging from the airing of the Radio Booster.
3. *Assess community members'/leaders' perceptions of the Radio Booster's influence:*
- a) How do listeners describe their engagement with the programme? (e.g. Which characters do they like/dislike? Which storylines resonate more/less?)
 - b) To what extent does listening prompt critical reflection, deepen reflection over *SASA! Together* ideas, influence new ways of thinking/acting/ etc?
 - c) Do listeners perceive the Radio Booster to have led to any changes in their intimate relationships, tolerance of violence, help seeking intentions/behaviours, level of personal activism? What role has the radio booster played in these changes?
 - d) Do listeners perceive that the Radio Booster has led to any changes in their relationships with others, beyond their intimate relationships, e.g., with children, extended family, community members etc.?
 - e) Do listeners perceive the Radio Booster to have led to any positive changes among others in the community (increased awareness/discussion of VAW, improved responses to VAW, activism, quality of intimate relationships, relationships with others, levels of violence, etc)?
 - f) Explore acceptability of Radio Booster content to community leaders, and the influence they perceive it to have had on institutional practices.
4. *Quantitatively assess change among community members (over the course of radio programming), in relation to:*
- o Attitudes relating to intimate relationships and the acceptability of IPV against women
 - o Quality of intimate relationships (trust, communication, decision-making, sexual decision-making etc.)
 - o Activism/intention to prevent or respond to IPV

and to compare this change between listeners/non-listeners. (Exposure levels permitting, this will be further broken down to compare outcomes in four exposure groups: Listen to radio + participate in *SASA! Together* community activities; Listen to radio only; Participate in community activities only; No exposure to radio or community activities.)

This research protocol henceforth outlines methods for the research component of the project.

Methods/design

Setting

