The evaluation is designed to assess the potential for the *SASA! Together* Radio Booster to strengthen the delivery and *potential* impacts of *SASA! Together* community programming. The main focus is on process related indicators (Objectives 1 to 3), but we will also chart indicators of attitude and behaviour change in the community over the course of implementation (Objective 4). The Radio Booster is in the early stages of development and it is important to understand its potential to strengthen VAW prevention initiatives before conducting a full-scale impact evaluation. Learning from the research will also be used to strengthen content in future iterations of the program.

The study will employ mixed methods to answer the specified objectives, including: repeated cross-sectional surveys of community members; and focus groups and in-depth interviews with

community members, listener groups, *SASA! Together* Community Activists, staff members involved in *SASA! Together*/Radio Booster implementation, and community leaders.

Community-member surveys

The quantitative component of the study will comprise two cross-sectional surveys of community members. The first (baseline) will be conducted approximately 6 weeks after the Radio Booster begins airing. The second survey (endline) will be conducted shortly after Radio programming finishes (approximately 37 weeks). At both time-points, the survey will measure indicators relating to the Radio-Booster's reach/listenership, and attendance/involvement in other *SASA! Together* activities. It will also measure indicators relating to: attitudes towards IPV and intimate relationships; quality of intimate relationships; and activism/intervention to prevent or respond to IPV.

Sampling strategy and sample size

At the first time-point (baseline) we aim to survey 650 community members (325 women and 325 men) aged 18 and above. At the second time-point (endline), we aim to survey 980 community members (490 women and 490 men) aged 18 and above. The endline sample size has been increased in relation to baseline due to freed-up resources from a cancelled midline survey, as detailed in the Protocol Amendments section below.

Sampling frame

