At the first time-point, we will conduct 24 IDIs with listeners (12 men and 12 women). At the second time-point, we will conduct 20 IDIs with listeners (10 men and 10 women). Listeners will be recruited from *SASA! Together* listener groups and will be purposively selected to represent different levels of listenership. Interviewers will conduct IDIs at the first time-point remotely, by telephone, rather than face-to-face (due to an Ebola outbreak affecting Western and Central Uganda, as detailed in the Protocol amendment section below). At the second time-point, interviews may be conducted by telephone or in person.

Potential participants will be identified by Community Activists operating in Kisinga subcounty. Community Activists will, with their consent, take the phone number of potential participants. These phone numbers will be shared with UGANET, who will share them with Research World International for the purpose of recruiting participants. Interviewers will telephone potential participants to explain the study and request their consent to participate in an IDI. If the potential participant chooses to participate, the interviewer will either conduct the IDI then or will arrange a future time and date to conduct the IDI. The interviewer will conduct the consenting process directly before conducting the IDI.

IDIs with community members will explore motivations/facilitators for listening to the Booster (Objective 1d) and barriers to listening (Objective 1e); community members' perceptions of the Booster's influence (Objectives 3a-e); the extent to which the Booster increases engagement with *SASA! Together* activities (Objective 2a) and reinforces *SASA! Together* messaging (Objective 2b); and safety issues around listening/radio content (Objective 2d).

Key informant interviews

KIIs will be held with Community Activists and staff from UGANET/ Raising Voices/ PVI. Key informants will be selected purposively to include those with extensive involvement and varied roles in intervention implementation and/or design.

Each Community Activist will be interviewed at two time-points – approximately 19 weeks after the Radio Booster begins airing, and shortly after Radio programming finishes (approximately 37 weeks). We will conduct 15 IDIs with Community Activists at the first time-point and 12 IDIs with Community Activists at the second time-point.

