KIIs with UGANET/ Raising Voices/ PVI staff and Community Activists will explore staff and community activists’ experiences of implementing the radio drama intervention (Objective 1h); the extent to which the Booster increases engagement with *SASA! Together* community activities (Objective 2a); the role of ‘listener groups’ in promoting critical thinking about Radio Booster content/facilitating links with *SASA! Together* ideas (Objective 2c); and ethical issues arising from implementation (Objective 2d).

Focus-group discussions

FGDs will take place with

- 2 ‘listener groups’ (1 female group, 1 male group)
- 2 groups of *SASA! Together* Community Activists (1 female group, 1 male group)

- 1 group of community leaders (cultural/religious/local government)

Each 'listener group' and group of Community Activists will take part in two FGDs, at approximately 6 weeks and 37 weeks after the Radio Booster begins airing. Repeated focus groups will allow assessment of how reception of and responses to the Booster change over time. The FGD with community leaders will take place at one time point (approximately 37 weeks) to allow reflection on the entire period of Radio Booster implementation.

Listener groups will be identified and selected with the help of *SASA! Together* Community Activists who have been involved in setting up and facilitating these groups. Activists to be interviewed will be purposively selected by UGANET to represent a range of ages, duration of involvement with the intervention and community characteristics. UGANET will also help identify community leaders (cultural, religious and local government) with whom they have had involvement during implementation of *SASA! Together* programming. Recruitment of all of these individuals into relevant focus groups will be conducted by Research World International in order to maintain the independence of the research process.

FGDs with listener groups will explore the acceptability and enjoyment of the Radio Booster content (Objectives 1d, 1e, 3a), the role of listener groups in promoting critical thinking about radio booster content/facilitating links with *SASA! Together* ideas (Objective 2c), and perceptions of the Radio Booster's influence within the community (Objectives 3c-3e).

FGDs with Community Activists will explore the same themes as those explored in the KIIs with programme implementers and CAs.

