UGANET and Raising Voices will create and update a referral list that includes formal and informal psycho-social-legal services for women experiencing VAW, including resources provided by UGANET (a helpline and shelter based in Kampala). This list is provided to all study participants irrespective of whether or not they have experienced VAW. If participants are taking part in remote IDIs or KIIs, they will be given the option to have the referral list shared with them by SMS. UGANET and Raising Voices will train research staff and programme facilitators on the use of the referral list. UGANET will have a dedicated staff member who will respond to new cases as they emerge. Programme activities will be monitored carefully for any signs of backlash.

Participants in study data collection who disclose any personal exposure to severe physical violence or sexual violence in the past year, or who report feeling unsafe and at risk of imminent violence, will be referred appropriately through UGANET established referral network including health, psychosocial, legal aid, shelter and other services.

Compensation

In line with the procedures of local ethics boards, as each session will take longer than 45 minutes, all participants in the study will be compensated with a token of appreciation for their time of the value of 10,000 Ugandan shillings (approximately 3 USD). All surveys participants will be offered a bar of a soap. FGD, IDI and KII participants will be offered 10,000 Ugandan shillings. In addition, FGD participants will be offered refreshments and, if they incur costs to travel to the site of the discussion, they will be reimbursed up to 10,000 Ugandan shillings.

As participation in listener groups is part of the implementation programme, we will not compensate participants in recorded listener groups.

For participants in IDIs and KIIs conducted remotely, compensation will be transferred to the participants in the form of mobile money. Participants will be reimbursed 11,000 Ugandan shillings to cover the mobile money withdrawal fee of 1,000 Ugandan shillings.

Protocol amendments

Several amendments have been made to the protocol since the study inception:

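### Objective 3e asks only about positive changes in others, and the open question on unexpected issues (2d) is not assigned to the listener focus groups, so evidence on community effects is tilted towards benefit

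*Protocol*

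**What the plan says.** Under Aims and objectives, Evaluation research, Objective 3e reads: "Do listeners perceive the Radio Booster to have led to any positive changes among others in the community". Its examples run from awareness and activism to quality of intimate relationships, relationships with others and levels of violence.

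Two neighbouring objectives are neutral. 3c begins: "Do listeners perceive the Radio Booster to have led to any changes in their intimate relationships, tolerance of violence". 3d begins: "Do listeners perceive that the Radio Booster has led to any changes in their relationships with others, beyond their intimate relationships". Objective 2d is the open harm-type objective: "Document any ethical /unexpected issues emerging from the airing of the Radio Booster".

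The Qualitative section assigns objectives to sources. In-depth interviews with listeners cover 3a to 3e among others, "and safety issues around listening/radio content (Objective 2d"). Key informant interviews with staff and Community Activists carry 2d, and the activist focus groups take the same themes. For the listener groups the text is: "FGDs with listener groups will explore the acceptability and enjoyment of the Radio Booster content (Objectives 1d, 1e, 3a"), followed by 2c and 3c to 3e. Objective 2d is not in that list.

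Ethics and safety adds: "Programme activities will be monitored carefully for any signs of backlash". It also provides a referral list for every participant and a staff member to respond to new cases.

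**The concern.** The protocol recognises that a respondent's partner may pose a risk and that backlash is possible. Its findings are meant to inform later versions of the Booster and whether a full-scale impact evaluation is worthwhile. For that decision, the account of what happened to other people in the community should be able to come out either way.

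Two features work against this. The objective about others asks for one direction only. The open question on unexpected issues goes to people tied to the programme: listener-group members whom activists put forward, and those who deliver the work. People for whom listening caused trouble at home may be less likely to join or stay in a listener group, or to be put forward by an activist. If the topic guides follow the objectives as written, favourable accounts of others will be gathered systematically and unfavourable ones only if someone volunteers them.

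**Working it through.** No stated sample size, power or precision figure is in dispute, so there is none to reproduce. The check traces each relevant objective to its sources.

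**Where 2d is asked**
- Listener in-depth interviews: 24 at about week 19 and 20 at about week 37. The design re-interviews the same people, so at most 24 different listeners. They come from listener groups and are identified by Community Activists.
- Key informant interviews: 15 + 12 = 27 with activists, plus 6 with staff, giving 33. All are implementers.
- Activist focus groups: 2 groups × 2 rounds (weeks 6 and 37) = 4 sessions. All are implementers.

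**Where 2d is not listed**
- Listener-group focus groups: 2 groups × 2 rounds (weeks 6 and 37) = 4 sessions, assigned 1d, 1e, 2c, 3a and 3c to 3e.
- Community-leader focus group: 1 session, assigned 3f, though its description also covers reception and influence in the community.
- Community-member surveys: the analysis section names 1a, b, c, f, g, 2a and 4.

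The focus groups total 4 + 4 + 1 = 9 sessions. Objective 2d is assigned to 4 of the 9, all with activists.

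**What the listener focus groups can yield about other people**
- 3c and 3d are neutral but concern the listener's own relationships.
- 1e concerns barriers to listening. It includes fear of being overheard and objection by others in the household, but a barrier to listening is not a consequence of it.
- 3e is the assigned objective about others, and it is limited to positive changes.

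So in these four sessions no assigned objective invites a report that things got worse for someone else. That matters most in a group, where a question about others can be answered without disclosing one's own situation.

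**Scale, as illustration only**
Suppose the interviewed listeners were a random sample and none reported trouble. The one-sided 95% upper limit on the proportion affected is 1 − 0.05^(1/n).
- n = 24: 1 − 0.05^(1/24) = 11.7%
- n = 20: 1 − 0.05^(1/20) = 13.9%
- n = 12 (first-round women): 1 − 0.05^(1/12) = 22.1%

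The chance that 24 interviews contain no case is (1 − p)^24. The documents give no value for p. At assumed values of 5% and 10% the chance is 29% and 8%. The sample is purposive, so these figures are not estimates of anything in this study. They show only that silence from so few people would not demonstrate rarity, even under ideal sampling.

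**The case against.** The strongest reply is that the protocol looks for harm in several places. Objectives 3c and 3d ask neutrally about any changes, in the interviews and in both rounds of listener focus groups, so listeners can report deterioration in their own relationships from week 6. The activist focus groups carry 2d from week 6, and activists live in these communities. Up to eight listener-group discussions are recorded between weeks 19 and 33. Objective 4 measures attitudes and relationship quality, which could move either way. The listener focus-group paragraph itself describes 3c to 3e as perceptions of influence within the community, which a topic guide could treat neutrally. All of this stands. It confines the wording fault to 3e and the assignment fault to 2d.

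A reader might go further and infer that the study barely looks for harm and could then report that there was none. The documents do not support that. Monitoring and referral are planned, nowhere is a finding of no backlash proposed, and the limitations section disclaims attribution.

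A reader might also infer that the surveys contain no question on unwanted consequences. The survey text lists domains, for example "It will also measure indicators relating to: attitudes towards IPV and intimate relationships". The questionnaire is a separate document and is not shown, so absence of an item cannot be established. Not asking directly about violence is a deliberate safety choice.

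Nor can the backlash monitoring be read as limited to in-person work, because the protocol also calls the broadcasts programming. A complaint that listeners are asked too late for content to be changed would miss as well, since the learning is directed to future iterations.

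What the objection leaves standing is that 3e is one-sided about others, and that the listener focus groups lack the open question.

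**Conclusion.** The point holds as a limited fault in wording and assignment. One objective asks about effects on others in the favourable direction only, although some of its listed outcomes can worsen. The open harm-type objective reaches only programme-linked respondents and is missing from all four listener focus-group sessions. The resulting evidence on community-level effects is tilted towards benefit and cannot support a statement that harm was absent or rare.

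The size of the tilt cannot be computed. The 11.7% limit shows scale under an optimistic assumption of random sampling and should not be cited as a property of the study. The conclusion assumes that the topic guides, which are not shown, follow the objectives as assigned. If they already probe for negative change in others, only the wording of the protocol needs correcting.

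**What to change.** 1. Reword Objective 3e so that it asks about any changes, positive or negative, among other people in the community.
2. Add Objective 2d to the listener-group focus groups in every round still to be held, at least the one at week 37. The amendments change only activities from week 19 onwards, so the week-6 round may already be past.
3. State in the report that these sources cannot estimate how often harm occurs.

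The cost is an edit to one objective, one addition to a topic guide, slightly longer discussions and possibly a few more disclosures, for which referral already exists.

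A neutral survey item on unwanted consequences of listening is optional. It comes close to the subject the survey avoids for respondents' safety, would need safety and ethics review, and may be too late for baseline.

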The study site is Kisinga Subcounty, comprising 25 villages (LC1). *SASA! Together* community programming is currently underway in 23 of these villages. From these 23, one will be purposively selected for questionnaire piloting based on logistical considerations. The other 22 will form the sampling frame for the community members survey. We will employ a multi-stage sampling strategy, with village as the primary sampling unit (PSU).

Sampling of villages

The original plan was to conduct the survey in all remaining 22 villages. However, this plan was modified due to seven of the villages being relatively inaccessible (3-4 hours walk from the next nearest village). For logistical purposes therefore, we decided to drop four of the less accessible villages from the sampling frame, while still retaining three of them in order to be able to estimate intervention reach to these more remote locations. Among the remaining 18 villages, stratified random sampling (stratifying by urban/rural and population size) will be used to select half of these (9) to form the basis of the sample of female community members. The other half (9) will form the basis of the male sample. This designation of male/female villages will remain the same for both survey timepoints to maintain comparability between survey rounds.

Sampling of households within villages

Allowing for failure to contact respondents, refusals to participate, and households without any eligible members, we will oversample households by 10% in order to achieve our target sample size of 650 respondents at baseline and 980 respondents at endline.

Within each village, 40 households will be sampled at baseline and 60 at endline. Different households will be sampled at each time-point, with the sampling strategy explicitly designed to avoid resampling the same households in multiple survey rounds. This both minimises respondent burden and eliminates the risks (discussed below) that might arise if two different members of the same household were selected to participate in the study in separate survey rounds.

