Households will be selected using systematic sampling based on the ‘random walk’ procedure from a central point in the village (identified with the help of local officials), with direction of travel established by spinning a bottle, and sampling interval pre-determined as 3. Selection of households for baseline, and listing of households (using GPS coordinates) for endline, will be undertaken during the same ‘random walk’, with endline households listed (and then randomly selected) from within the baseline sampling interval. This will ensure that both samples are drawn from the same neighbourhoods. Interviewers will continue in a village until they have selected and attempted to contact the target number of households. No substitutions will be made where interviewers are unable to make contact with a selected household or where households refuse to participate.

Sampling of individuals within selected households

We will randomly select one eligible person from each selected household to participate in the survey. A household selection form will be used to ascertain whether the selected household has any members eligible to complete the community member survey. Where more than one eligible household member is identified, one will be randomly chosen for interview (with no substitutions made for refusals or failure to subsequently contact this person).

The limit of one survey respondent per household, and the use of single sex samples in any given village, are designed to maximise respondent safety. While we will not ask directly about experience/perpetration of VAW, a woman could still potentially be put at risk if other members of the household/neighbourhood know she is participating in a survey about a violence prevention intervention and have concerns about potential disclosures she might make.

Study precision/power

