- Seven of the 22 villages in the original survey sampling frame were more remote than anticipated (3-4 hours walk from the next nearest village). For logistical purposes therefore, we decided to drop four of the less accessible villages from the sampling frame, while still retaining three of them in order to be able to estimate intervention reach to these more remote locations. The survey will now take place in a total of 18 villages.

Furthermore, an Ebola outbreak in the Western and Central regions of Uganda (September 2022 – January 2023) led to the following changes to the protocol:

- Cancellation of a planned midline survey of community members. Initially we planned three surveys (baseline, midline and endline), but this has now been changed to two surveys (baseline and endline).
- Larger sample size for the community-member survey at endline. Resources originally intended for the midline survey will be diverted towards the endline survey. We originally planned to survey 650 people at each of the three planned time-points. With cancellation of the midline, our endline target sample size has now been increased to 980.
- Change to remote data collection for first round of IDIs and KIIs (conducted approximately 19 weeks into Radio Booster programming). Originally these were intended to be conducted face-to-face, but will now be conducted over the telephone.
- Cancellation of middle round of FGDs with listener groups and CAs. Originally three rounds of FGDs were planned, but the round planned for 19 weeks into programming has now been cancelled.
- Listener group recordings (not originally planned) will now be instigated in lieu of the cancelled round of FGDs with listeners.

Dissemination strategy

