The rationale behind this approach comprises the following: In order to demonstrate incremental impacts of the Radio Booster over and above SASA! Together community programming, a large number of communities and a lengthy follow-up period would be required. The Radio Booster is in the early stages of development and it is important to understand its potential to strengthen VAW prevention initiatives before investing the level of resources that a full-scale impact evaluation would entail. Furthermore, random allocation of sites to intervention or control arms would not be feasible given the large geographic areas covered by radio stations.

Our study also has many strengths. We employ mixed methods to quantify and *understand processes of* intervention uptake and diffusion, synergies between intervention components, and attitudinal and behavioural change among community members. The quantitative survey is conducted among a quasi-random sample of community members. While a true random sample is not feasible given the absence of up-to-date household lists, the quasi random sampling strategy should minimise selection bias and ensure that the sample is representative of the wider study community. Selection bias can also occur through non-response. Response rates in this study will be maximised in a number of ways: at least three repeat visits will be made to households where

respondents are not available at the time of the first visit; interviewers will be trained on how to introduce the study and build rapport with respondents in order to minimise the number of refusals; the cross-sectional design precludes the problem of loss to follow-up between survey rounds. Repeated community surveys allow us to assess how listenership and outcomes change over time.

The inclusion of non-listeners as well as listeners in our sample allows us to examine barriers to listening, as well as explore whether attitudinal and behavioural outcomes differ between listeners and non-listeners. Though this type of comparison is prone to self-selection bias if underlying differences exist between listeners and non-listeners, thereby impeding causal attribution to the Radio Booster, taken together with evidence on process it adds to the plausibility assessment of the potential for this type of intervention to reduce IPV.

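### A fixed interval of 3 ends each village walk after about 120 dwellings in both rounds, so coverage of larger villages is incomplete and the claim of a representative sample is not secured

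*Protocol*

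**What the plan says.** The Protocol describes the walk under Sampling of households within villages. It starts at a central point found with the help of local officials, "with direction of travel established by spinning a bottle, and sampling interval pre-determined as 3". The number to select is the same everywhere: "Within each village, 40 households will be sampled at baseline and 60 at endline". The stopping rule is "Interviewers will continue in a village until they have selected and attempted to contact the target number of households". The second round uses the same walk, "with endline households listed (and then randomly selected) from within the baseline sampling interval".

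Sampling of villages uses population size as a stratifier when villages are split into male and female samples, so villages are known to differ in size. No household counts are given. No rule adapts the interval to village size, adds further starting points or segments, or says what happens when the walk reaches the village edge.

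Strengths and limitations concedes that the sample is only quasi-random, for want of current household lists. It then states that "the quasi random sampling strategy should minimise selection bias and ensure that the sample is representative of the wider study community".

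**The concern.** A systematic sample covers its whole frame only if the interval is about the frame size divided by the number of selections. Here both the interval and the number are constants, so the stretch walked is also a constant, while the villages vary. In a village larger than that stretch the walk stops before the village is covered. Because endline is nested in the baseline walk, the larger endline sample raises the sampling density within the stretch but adds no coverage.

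This matters for Objective 1, on which the sample size section bases its precision and power. The Protocol itself treats distance as relevant to reach: the booster is meant for isolated communities and people with restricted mobility, and three remote villages were kept so that reach there could be estimated. Objective 1f also counts exposure to in-person activities, and Listening Groups meet in person. Both could vary with where in a village someone lives, even if the radio signal does not. Later weighting would need selection probabilities, and the described procedure supplies none for dwellings that the walk never passes.

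**Working it through.** **Inputs (all from the Protocol).** Interval 3; 40 baseline and 60 endline households per village; central start and one spun direction; endline drawn from skipped dwellings; 18 villages ("The survey will now take place in a total of 18 villages"); 10% household oversampling for targets of 650 and 980 ("we will oversample households by 10% in order to achieve our target sample size of 650 respondents at baseline and 980 respondents at endline"). Not given: the number of households in a village, V, and any difference in listening between walked and unwalked parts, d. Both are assumed below.

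**1. The plan's own household numbers.** 18 × 40 = 720 and 18 × 60 = 1,080. Adding 10% gives 650 × 1.1 = 715 and 980 × 1.1 = 1,078. Dividing by 0.9 gives 722 and 1,089. Either way, 40 and 60 per village fit the targets.

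**2. Length of the walk.** 40 × 3 = 120 dwellings, or (40 − 1) × 3 + 1 = 118 counted from first to last selection. V does not enter.

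**3. Room for endline.** Skipped dwellings: 40 × (3 − 1) = 80, of which 60/80 = 75% are needed. An interval of 2 would leave only 40 × 1 = 40, which is too few. So 3 is the smallest whole interval that serves both rounds.

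**4. Share of a village passed**, min(1, 120/V), and the interval that would span it, V/40:

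| V (assumed) | Share passed | Dwellings not passed | V/40 |
|---|---|---|---|
| 120 | 100% | 0 | 3 |
| 150 | 80% | 30 | 3.75 |
| 200 | 60% | 80 | 5 |
| 300 | 40% | 180 | 7.5 |
| 400 | 30% | 280 | 10 |

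Below 120 households coverage is not the issue, but one pass at interval 3 yields fewer than 40 selections (V = 100 gives 33).

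**5. What this could do to one village's estimate.** Bias = (1 − 120/V) × d, taking the sign of d:

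| V (assumed) | d = 5 points | d = 10 points | d = 20 points |
|---|---|---|---|
| 150 | 1 | 2 | 4 |
| 200 | 2 | 4 | 8 |
| 300 | 3 | 6 | 12 |

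**6. Overall estimate.** With the same number of households selected in every village, the overall bias is roughly the average over villages. Suppose 9 of the 18 villages had 200 households, the other 9 had 120 or fewer, and d were 10 points with the same sign throughout. Then the overall bias is (9 × 4 + 9 × 0)/18 = 2 points. Table 1's margin at 50% prevalence and DE = 1 is reproduced by 1.96 × √(0.25/650) = 3.84 points. The single-village figures in step 5 should not be set against that overall margin.

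**The case against.** A reader might infer that outlying households can never be selected. The documents do not support that. The direction is random, so before the spin a distant dwelling on a possible path has some chance, and a walk of 120 dwellings in one direction may reach the village edge. What is missed may lie largely in other directions, including near the centre.

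A reader might also infer that every village is affected. Stratifying on population size shows that sizes vary, not that any village exceeds 120 households, and a village of about 120 or fewer can be walked in full.

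A third tempting inference is that reach is overestimated. No data on listening by location are given, and Study precision/power expects high radio coverage throughout the site. Differences between walked and unwalked parts could also partly cancel over 18 randomly directed walks.

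Further points in the plan's favour are that it admits quasi-random sampling, handles remoteness between villages by keeping three remote ones, and is a process-oriented pilot that disclaims attribution. Turning and boundary rules may sit in field instructions that are not shown.

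All of this limits the size of the point. It does not change the fixed 120-dwelling stretch or the confinement of endline to it. Uniform radio coverage does not settle in-person exposure, and admitting a quasi-random sample does not support a statement that representativeness is ensured.

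**Conclusion.** The point stands as a coverage risk, not as demonstrated bias. It follows from the stated rules that each walk passes about 120 dwellings regardless of village size and that both rounds share that stretch. In any village above about 120 households, part of the village is out of reach in both rounds once the direction is spun, and selection probabilities are unequal and unknown.

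How many villages this affects, and the size and direction of any effect on reach, cannot be known from the Protocol. The shares of 80%, 60% and 40%, and the illustrative overall 2 points, rest on assumed village sizes and an assumed 10-point gap of constant sign. The firm conclusion is that the statement on representativeness in Strengths and limitations goes further than the sampling rule allows.

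**What to change.** Replace the single interval of 3 with a village-specific one: approximate number of households divided by 40, using the size information already held for stratification, with a minimum of 3 so that enough skipped dwellings remain for endline. State that the walk continues until it has spanned the village, and what interviewers do at the edge. Draw endline at random from the skipped dwellings as now, which keeps the two rounds in the same neighbourhoods without overlap. Approximate counts suffice, so the lack of current household lists is no bar.

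The cost is more walking and more GPS listing in larger villages; no interviews are added. The targets of 40 and 60 should not be cut in small villages: 720 and 1,080 households leave only about 10% of slack over 650 and 980.

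The baseline walk has probably been done, since baseline falls at about week 6 and the Protocol amendments already record changes to later rounds. In that case, use the GPS listing with approximate household counts to report the share of each village covered, and limit the statement in Strengths and limitations to the walked areas. That costs almost nothing.
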